### 5.3 Description of Baseline

For all treatment groups and under both designs, the baseline is defined as the last available, non-missing, value before or on Study Day 1. Study Day 1 is defined as the day of dosing (or the day of randomization for subjects randomized and not dosed).

At Week X, absolute change from baseline will be defined as value at Week X – baseline value.

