8.0 STUDY DRUG

8.1 Study Drug Administration

Both GB0139 (3 mg) as well as the placebo will be administered via inhalation once a day using the Plastiaple RS01 Monodose DPI device (a CE marked device).

All subjects must be trained in the use of the inhaler device at w0/baseline, according to the instructions provided with the device ([Appendix 1](#) in Section 18.0). Placebo capsules and inhaler devices will be provided for training and demonstration purposes. Site staff should be assured the subject will be able to administer the drug at home safely and competently. The same DPI devices can be used for training throughout the study but must not be used for dosing. Study site personnel will dispense the IMPs, and site personnel will facilitate administration when the subject is in the clinic, at the time of w0/baseline, however subjects themselves will hold the DPI device during inhalation. At subsequent visits up until study completion/withdrawal the subject's technique with the DPI device should be assessed to ensure correct usage and further instruction given if required/requested.

Capsules will be loaded into the DPI device as per the instructions provided with the device (and included in [Appendix 1](#)). A single device will be used per two weeks of dosing. The device will be dispensed with the IMP. One (1) to three (3) inhalations from the DPI device will be performed with each capsule. Any problems with drug administration will be noted in the CRF.

Site staff will instruct the subject on how to take the drug, including the number of capsules to be inhaled each day and the timing of dose administration. On administration of the first dose the subject should be monitored at the site for 1 hour to observe any acute adverse reaction to study medication (e.g., bronchospasm). The PI/attending physician may perform additional spirometry as part of their assessment if, in their opinion, it is safe to do so and would be helpful in the assessment of any such events. For daily doses taken at home, subjects should be advised to administer the study drug at approximately the same time of day. Subjects will be given DPI devices and enough supplies until their next visit (plus one week). Subjects will be encouraged to contact the site for additional advice and support if they have an issue whilst using the inhaler.

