14.4.1 Analysis of Primary Efficacy Endpoint

The primary endpoint is described in Section 9.1. The primary efficacy analysis is a random coefficient regression (random slopes and intercepts) model. Treatment and baseline FVC (mL) will be included as a covariate in the analysis model. Other covariates such as age, and gender will be included as covariates unless their inclusion violates model assumptions or impacts stability. Baseline FVC is defined as the FVC result recorded at Visit w0/baseline, unless missing in which case the latest FVC before randomization in the subject's chart result will be used.

The decrease in FVC is assumed to be linear within each subject over 52 weeks. The intercepts and slopes will be assumed to be normally distributed with arbitrary covariance matrix. The within-subject error will be assumed to be independent and normally distributed with mean zero and a common variance. The Kenward-Roger approximation will be used to estimate denominators degrees of freedom.

Section 14.8 details of the approaches to handling of missing data are given.

Significance tests will be based on least-squares means; p-values and two-sided 90% confidence intervals for the difference between the treatment groups will be presented. An intent-to-treat principle will be used. Analyses will be implemented using SAS® Version 9.4 or higher. The assumptions for the primary analysis of decline in FVC will be tested; details will be provided in the SAP. The primary analysis will be based on observed data (but including retrieved drop out

measurements) and will assume remaining missing data are missing at random. The effect of missing data will be investigated using multiple imputation methods which assume that subjects who discontinue treatment will no longer benefit from it in the future. See Section 14.8 for further details of these sensitivity analyses.

Subgroup analyses will be fully specified in the SAP and will include:

- Age
- Gender
- Race
- Ethnicity
- Previous treatment with pirfenidone and/or nintedanib
- Recruitment cohort (e.g., pre- or post- DSMB cutoff, and pre- or post-Protocol version 6.1_UK)

A cumulative distribution plot will be provided, showing the percentage of subjects by change from baseline in FVC in mL at week 52.

Data will be summarized graphically and using summary statistics.

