#### **7.3.1 Exposure and Treatment Compliance**

Details of exposure and treatment compliance will be summarized for the mITT Analysis Set, as well as for the Safety Analysis Set. In addition, for the Primary Population only, exposure and compliance will be summarized in the PP Analysis Set.

Date of first dose of study treatment will be derived as the earliest date of drug dispense from the ‘Treatment Compliance’ eCRF forms.

Extent of exposure to GB0139 (mg) or Placebo will be calculated based on information from the ‘Treatment Compliance’ eCRF forms. The number of capsules used will be derived as the number of GB0139 capsules dispensed minus the number of unused GB0139 capsules returned during the study. The number of GB0139 capsules used and the dose of GB0139 in the capsules known to have been dispensed will be used to derive the extent of exposure (mg) to GB0139.

	Plus-Project Statistical Analysis Plan	
	Protocol Number: GALACTIC-1	Version: 1

The duration of exposure to GB0139 in days will be calculated as the date of last dose recorded in the 'Disposition Study Completion' eCRF minus the date of first dispensing of GB0139 + 1.

The duration of exposure to GB0139 will be summarized both as a continuous variable and categorically, with categories 0-13 weeks, >13 weeks – 26 weeks, >26 weeks=39 weeks, >39 weeks – 52 weeks, > 52 weeks.

The extent of exposure (mg) will be summarized as a continuous variable by treatment group.

The extent (mg) and duration of exposure (days) between each dispensing and returning of study drug will be presented in the listings but will not be summarized.

The duration of exposure to nintedanib or pirfenidone during treatment with study drug will be derived based on the start and stop dates of nintedanib and pirfenidone from the 'Pirfenidone/Nintedanib Usage' eCRF and the first and last date of study drug.

The expected treatment exposure (capsules) will be derived using the treatment duration with study drug multiplied by 2 (the planned daily number of capsules).

Treatment compliance based on dispensing data will be derived as 100 x treatment exposure (capsules) / expected treatment exposure for duration of study treatment through study treatment discontinuation (capsules).

The treatment exposure to study drug (capsules), treatment duration with study drug (days) and treatment compliance (continuous and grouped as < 80%, 80% to 120%, > 120%) will be summarized.

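### SAP 5.3 sets baseline by calendar date with no pre-dose condition, so a post-dose Day 1 FVC could become baseline, and it departs from protocol 14.4.1 without saying so

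*SAP*

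**What the plan says.** - **SAP 5.3** applies one rule to all variables, treatment groups and both designs: "the baseline is defined as the last available, non-missing, value before or on Study Day 1". Study Day 1 is the calendar day of dosing, or of randomization for subjects never dosed. No time of day or order relative to the dose is mentioned.
- **SAP 7.3.1** fixes the first-dose date from dispensing records: "Date of first dose of study treatment will be derived as the earliest date of drug dispense".
- **SAP Table 1 (section 5.2)** gives the baseline visit no analysis window, so section 5.3 alone decides which reading is used.
- **SAP 7.2.1** takes FVC from an external spirometry vendor and bases the analyses on every FVC value obtained, dropping only those after Day 453.
- **Protocol Table 1** schedules spirometry and the first in-clinic dose at the same visit, Visit 2. Protocol 8.1 confirms that "site personnel will facilitate administration when the subject is in the clinic, at the time of w0/baseline".
- **Protocol 8.1** continues: "On administration of the first dose the subject should be monitored at the site for 1 hour", to look for acute reactions such as bronchospasm. It adds that "The PI/attending physician may perform additional spirometry as part of their assessment", subject to the physician's view of safety and usefulness.
- **Protocol 14.4.1** defines the baseline for the primary endpoint in other words: "Baseline FVC is defined as the FVC result recorded at Visit w0/baseline, unless missing in which case the latest FVC before randomization".
- **SAP section 9**, which lists departures from the protocol analysis, does not mention baseline.

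**The concern.** On Day 1 a subject may have two FVC readings: the scheduled one and another taken because a reaction to the first inhalation was suspected. A rule that takes the last reading of the day picks the second. That reading may be depressed by the very event it was taken to assess, and it is not a pre-treatment value.

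A baseline that is too low makes later decline look smaller. Baseline FVC enters the primary model twice, inside the change score and as a covariate (SAP 7.2.2 and 11.5.1). It also feeds the FVC MMRM (SAP 7.2.2.4), the change plots, and the responder endpoints at 10 and 5 percentage points of predicted FVC (SAP 7.2.3.1 and 7.2.4.1). The error would fall only on subjects who had a Day 1 reaction.

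The SAP handles same-day ordering elsewhere: section 7.3.2 uses a before/after-first-dose item to classify adverse events starting on the first dispensing date. Baseline has no equivalent. Because section 5.3 covers all variables, Day 1 vital signs, ECG, laboratory and biomarker values have the same gap, although protocol 14.5.2 wants safety findings compared with those from before the start of treatment.

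**Working it through.** **1. The plan's own figure.** Protocol 14.6 gives 75% power for N = 141, a difference of 100 mL, SD 240 mL, two-sided 10% and 2:1 allocation. Taking 94 and 47 subjects (2:1 applied to all 141): SE = 240 × √(1/47 + 1/94) = 42.9 mL; 100/42.9 = 2.33; 2.33 − 1.645 = 0.69; power = 75.4%. The figure reproduces. The baseline definition does not enter it, so it serves only as a yardstick: the planned difference is 100 mL.

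**2. The two rules side by side.**
- One reading on Day 1, taken before the dose: both rules give that reading.
- No reading on Day 1: both normally fall back to the latest earlier value, although the protocol's limit is randomization and the SAP's is the end of the dosing day.
- Two readings on Day 1, one after the dose: the SAP takes the later one. The protocol says the result recorded at Visit w0, without saying which one or that it must be pre-dose.

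The rules therefore clearly differ only in the SAP's choice of the last reading and in the fallback wording. I found nothing in either document that orders spirometry before dosing or excludes a post-dose Day 1 reading.

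**3. Shift in mean change from baseline.** The documents give no reaction rate or size, so these are assumptions: a fraction f of one arm has a Day 1 value D mL below the pre-dose value. Shift in that arm = f × D.
- f = 1%: 1, 2 and 4 mL for D = 100, 200 and 400 mL.
- f = 3%: 3, 6 and 12 mL.
- f = 5%: 5, 10 and 20 mL.

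The treatment difference moves by (f × D in active) − (f × D in placebo). With f = 5% and D = 400 mL in both arms this is 20 − 20 = 0. With only one arm affected it is at most 20 mL, in favour of that arm.

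**4. Primary slope.** A baseline that is D too low adds D to every post-baseline change. A least-squares line through weeks 4, 8, 12, 26, 40 and 52 then has slope shift 0, because the constant goes to the intercept. If a zero-change record at time 0 is also modelled, the slope shift is D × 0.390/0.859 = 0.454 × D, where 0.390 is the sum of post-baseline deviations from mean time and 0.859 the sum of squared deviations, in years. At arm level: 0.01 × 0.454 × 100 = 0.5 mL/year up to 0.05 × 0.454 × 400 = 9.1 mL/year. This is a simple fit, not the planned mixed model, and serves as a guide to size only.

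**5. Responder endpoints.** Assume 3000 mL predicted. Then D = 100, 300 and 400 mL correspond to 100/3000 = 3.3, 300/3000 = 10 and 400/3000 = 13.3 percentage points. With D = 300 mL, status at the 10-point threshold changes only for an affected subject whose true decline is above 10 and up to 20 points. Affected subjects number 0.01 × 94 = 0.9 to 0.05 × 94 = 4.7 in the active arm, or 0.01 × 47 = 0.5 to 0.05 × 47 = 2.4 in placebo, and only some of them would lie in that band.

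**The case against.** The strongest reply is that the problem may never arise. It needs a reaction within the hour, a physician who chooses optional spirometry, and a result that reaches the vendor's dataset. Protocol 10.4.13 says spirometry is centrally evaluated, but neither document says whether an ad hoc safety reading is transmitted or kept. This stands: a post-dose baseline is possible, not routine.

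A reader might infer that the protocol has a clean pre-dose rule which the SAP breaks. The documents do not support that, because the Visit w0 wording is silent on dosing.

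A reader might also infer a bias in favour of GB0139. That is unsupported too. Both arms inhale two capsules a day, all subjects are observed after the first dose, protocol 6.5 reports 3 mg as well tolerated, and protocol 8.6 expects no drug-specific side effects. If reactions come mainly from inhaling powder, the shifts largely cancel and what remains is noise.

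The blinded data review meeting (SAP 4.6) is to settle SAP definitions before lock and could resolve duplicate Day 1 readings. That is a real backstop, but an ad hoc one. The rule as written already gives an answer, so nothing would prompt the meeting to look.

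Finally, the date-based wording has a likely reason. A strict before-first-dose rule applied to dates would throw away valid Visit 2 readings. This also stands and shapes the fix.

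**Conclusion.** The gap is real but minor. As written, SAP 5.3 would select a post-dose Day 1 FVC over the pre-dose value if both were in the data, and the departure from protocol 14.4.1 is undeclared.

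Under the assumed range, the shift is 1-20 mL in one arm's mean change, against a planned difference of 100 mL, and near zero between arms if both react alike. It bears mainly on the responder endpoints, the FVC MMRM and the change summaries. It would be wrong to read it as a threat to the primary result: the slope shift is nil if only post-baseline visits are modelled and about 0.5-9 mL/year in one arm otherwise.

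The sizes rest on assumed rates and reductions. The direction assumes that the post-dose reading is the lower one. The comparison uses the supplied protocol, which refers to version 6.1_UK, whereas the SAP cites version 7.0.

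**What to change.** In SAP 5.3, define baseline as the last non-missing value before the first dose of study drug, identified by assessment time or by a before/after-dose flag. Do not apply it by date alone: first dose is derived as a dispensing date, so a date comparison would discard valid Visit 2 values. For subjects never dosed, the present rule can stay, since no post-dose value can exist.

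For FVC, name the scheduled pre-dose Visit 2 reading, exclude unscheduled post-dose spirometry on Day 1 from the choice of baseline, and fall back to the latest earlier value if the Visit 2 reading is missing.

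Then either align the wording with protocol 14.4.1, adding pre-dose there too at the next opportunity, or list the change in SAP section 9.

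The cost is small but not nil: Day 1 assessments need a time or a pre/post flag, and it should be checked that the spirometry vendor's data carry one. Sample size and power are unchanged. The change should be made before database lock and unblinding, when the SAP is due to be finalized, so that nobody chooses between two Day 1 values afterwards.

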### 5.4 Tables, Listings and Figures Presentation

All outputs will be incorporated into PDF files, sorted and labelled according to the ICH recommendations, and formatted to the appropriate page size(s).

For all outputs, the order and labels of the treatment groups will be displayed as per Table 2 below:

**Table 2: Ordering and labelling of treatment groups for each population**

Primary Population	SoC1 / Combination Population	SoC2 / Monotherapy Population
Placebo GB0139 3mg Total *	Placebo GB0139 3mg GB0139 10mg Total*	Placebo GB0139 3mg GB0139 10mg Total*

\*Where applicable.

Table 3 shows the study visit labels to be used in the listings.

	Plus-Project Statistical Analysis Plan	
	Protocol Number: GALACTIC-1	Version: 1

**Table 3: Study visit labels**

Visit Number (Title)	Visit Label
Visit 1 (Screening)	Screening
Visit 2 (Baseline / Randomization)	Baseline
Visit 3 (Week 4)	Week 4
Visit 4 (Week 8)	Week 8
Visit 5 (Week 12)	Week 12
Visit 6 (Week 26)	Week 26
Visit 7 (Week 40)	Week 40
Visit 8 (Week 52)	Week 52
Follow-up Visit 1 (Week 76) [a]	Week 76 (FUV1)
Follow-up Visit 2 (Week 104) [a]	Week 104 (FUV2)
Follow up telephone call [b]	Follow-up call
Unscheduled	Unscheduled

[a] Applicable to subjects in the SoC1 / Combination and SoC2 / Monotherapy Populations only

[b] Applicable to subjects in the Primary Population only

The listings will display all the data contained in the EDC system. All screen failure information will be listed separately. The listings will be ordered by strata, treatment group, site, subject, visit and visit date unless otherwise stated. All AE listings will contain age, sex, weight and race.

Summaries for continuous variables will use the descriptive statistics as described in Section 5.1. The number of decimal places to be displayed for each will be as follows:

- Mean, median, 25th percentile and 75th percentile: one more decimal place than source data.
- Standard deviation, coefficient of variation: two more decimal places than data.
- Minimum and maximum: same number of decimal places as data.
- Confidence intervals: 2 decimal places.
- P-value: 3 decimal places, if less than 0.001 then display as “<0.001”.

Categorical variables will be presented as frequency counts and percentages. Percentages will be displayed to one decimal place throughout in the Tables, Figures and Listings (TFLs). If the count is 0, the percentage will not be displayed.

All dates will be displayed in the format DDMMYYYY.

	Plus-Project Statistical Analysis Plan	
	Protocol Number: GALACTIC-1	Version: 1

Calculations using dates will follow these conventions:

- The relative study day of the event (DAY) is calculated as the difference between the date of the event of interest (EVENT DATE) and reference start date, where reference start date is defined as the date of first dose of study medication for all subjects, i.e.  
 $DAY = EVENT DATE - REFERENCE START DATE + 1$  for  $EVENT DATE \geq REFERENCE DATE$   
 $DAY = EVENT DATE - REFERENCE START DATE$  for  $EVENT DATE < REFERENCE DATE$
- Durations will be calculated by:  $DURATION = (STOP DATE - START DATE) + 1$

## 6. DEMOGRAPHIC AND BASELINE CHARACTERISTICS

### 6.1 Subject Disposition

Subject disposition data will be presented by randomized treatment group.

The following will be summarized for each of the populations based on the ITT Analysis Set unless otherwise stated:

- Subjects screened, screen failed (including reasons), randomized, randomized after re-screening, randomized and not dosed, and dosed (Screened Set). For this output only, a total column will also be included.
- Treatment completion (including reasons for discontinuation).
- Study completion (including reasons for discontinuation).
- Major protocol deviations will be summarized by category and whether they lead to exclusion from the PP Set.
- Analysis sets (including reasons for exclusion).

Specific details related to study treatment discontinuation and study discontinuation captured as free text fields in the CRF will be listed only.

Supportive listings will be provided for all subjects (including screen failures); date of informed consent, date of informed re-consent, randomization (yes/no), date of randomization and, where available, reasons for non-randomization will be included.

Violation of inclusion/exclusion criteria will be listed.

	Plus-Project Statistical Analysis Plan	
	Protocol Number: GALACTIC-1	Version: 1

## 6.2 Demography and Baseline Characteristics

The following demographic and baseline characteristic variables will be summarized (with unit for continuous variables or categories for categorical variables) for the ITT, mITT and PP Sets:

- Age (complete years) from eCRF
- Age group (<70 years / >= 70 years)
- Gender (Male/ Female)
- Race (American Indian or Alaska Native/ Asian/ Black or African American/ Native Hawaiian or Other Pacific Islander/ White/ Other)
- Ethnicity (Hispanic or Latino/ Not Hispanic or Latino)
- Country (Australia/ Belgium/ Canada/ France/ Georgia/ Germany/ Ireland/ Israel/ Italy/ Poland/ Russia/ Spain/ Ukraine/ United Kingdom/ United States). This will be derived from the country code in the subject number.
- Height (cm)
- Weight (kg)
- Body Mass Index (kg/m^2) [derived in the eCRF]
- Smoking Status (Current-smoker/ Ex-smoker/ Never smoked)
- Diagnosis Confirmed from HRCT for Fleischner criteria (Yes/ No)
- Pirfenidone or Nintedanib Usage at Screening (Current/ Previous/ Never)
- SoC Randomized Strata (SoC1 / SoC2) – per randomization
- Forced Vital Capacity (mL)
- 6-Minute Walk Test Total Distance (m)
- DLCO corrected for HB (mmol/min/kPa)
- UCSD – SOBQ Total Score
- SF-36 Total Score
- SGRQ Total Score
- Serum galectin-3 at baseline

Medical History (split by prior / ongoing) and Prior / Concomitant Medications will be described by frequency tables for the Safety Set.

The number of subjects randomized at each country and site will be summarized by treatment group for the ITT.

All summaries (other than those in the PP Set) will be repeated for the SoC1 /Combination and SoC2 / Monotherapy populations and supportive listings will be provided.

	Plus-Project Statistical Analysis Plan	
	Protocol Number: GALACTIC-1	Version: 1

### 6.3 Prior and Concomitant Medication (excluding pirfenidone and nintedanib)

Data relating to medications other than pirfenidone or nintedanib will be presented according to data collected in the 'Prior and Concomitant Medications' page of the eCRF and will be coded using the most recent upversioned World Health Organization (WHO) Drug Dictionary as specified in the Data Management Plan (DMP).

Each medication will be assessed for whether it was prior medication, concomitant medication or medication taken post-treatment.

For partial/missing dates, the following approach will be taken:

- Prior medication: If the stop month/year (if day is missing) or year (if day and month are missing) of the medication is prior to the respective month/year or year of the first dose of study drug then the medication will be classed as prior.
- Medications taken post-treatment: If the start month/year (if day is missing) or year (if day and month are missing) of the medication is after the respective month/year or year of the date of discontinuation of study drug then the medication will be classed as taken during follow-up.
- Otherwise, the medication will be concomitant.

Subject incidence of prior and concomitant medication (excluding pirfenidone and nintedanib usage (separate summaries)) will be summarized for the Safety Analysis Set by Anatomic Therapeutic Class (ATC) 1, ATC 3 and preferred name as well as overall. Summaries will be presented by ATC 1, ATC 3 and preferred name, sorted by decreasing frequency over all subjects and then alphabetically. Subjects will be counted only once for each ATC code or preferred name, if they have multiple records of the same ATC codes or preferred name in the database.

Summaries will be repeated for both the SoC1 / Combination and SoC2 / Monotherapy Populations and a listing will be provided. Medications taken post-treatment will be listed only.

